7.3 EXPLORATORY ENDPOINTS

Endpoints related to nutritional status

- Changes from baseline in lean body mass, bone mineral content and fat mass by Dual-Energy X-ray Absorptiometry (DEXA) scan from baseline at Weeks 4, 24, and 48
- Change in body weight from baseline at Weeks 4, 24, and 48 (applicable to the protocol version 4)
- Change in body weight from baseline at Weeks 24 and 48 (applicable to the protocol version 3)
- Change in dietary intake of wet weight (oral solid food, oral fluid), energy, macronutrients, and electrolytes (sodium, potassium, calcium and magnesium) from baseline at Weeks 4 and 48
- Change in fecal excretion of wet weight (feces), energy, macronutrients, and electrolytes (sodium, potassium, calcium and magnesium) from baseline at Weeks 4 and 48

Endpoints related to efficacy

- Change from baseline in the total time per day that subjects infuse PS at Weeks 24 and 52
- Change from baseline in the total time per week that subjects infuse PS at Weeks 24

and 52

- Change in electrolytes, minerals, macronutrients and other contents of the PS from baseline at Weeks 24 and 52

Patient Reported Outcomes

- Short Bowel Syndrome with Intestinal Failure and Colon-in-Continuity - Changes from baseline in Quality of Life Questionnaire (SBS-IF-CIC-QOL) at Weeks 24 and 52
- Short Bowel Syndrome with Intestinal Failure - Observed scores in Treatment Impacts - Quality of Life Questionnaire (SBS-IF-TI-QOL) at Weeks 24 and 52

[REDACTED]

- [REDACTED]
- [REDACTED]
- [REDACTED]
- [REDACTED]
- [REDACTED]
- [REDACTED]
- [REDACTED]
- [REDACTED]
- [REDACTED]
- [REDACTED]
- [REDACTED]
- [REDACTED]

8. ANALYSIS POPULATIONS

Analyses of efficacy and PRO will be based on the Full Analysis Set (FAS; See definition below), whereas all the rest of analyses will be based on the Safety Analysis Set (SAS; See the definition below), except for the summary table for all screened subjects and for the disposition table, which will be based on SAS as well as FAS.

To help characterize the FAS, tables for demographics & other baseline characteristics, concomitant diseases and medications, and treatment exposure & compliance will be repeated by FAS. The additional changes to this plan can be found in [Appendix 4: Addendum to Statistical Analysis Plan](#).

8.1 FULL ANALYSIS SET

FAS will comprise all subjects who have received at least one dose of trial treatment and contributed at least one valid post-baseline efficacy point.

8.2 SAFETY ANALYSIS SET

SAS will comprise all subjects exposed to trial medication.

9. Analytical Plan and Statistical Methods

9.1 GENERAL CONVENTIONS AND STATISTICAL CONSIDERATIONS

The statistical evaluation of the trial will include descriptive statistics of the primary and secondary endpoints reflecting the exploratory nature of the trial. In addition, simple analyses will be provided for efficacy endpoints and PRO.

Descriptive statistics for continuous variables will include the number of subjects, mean and standard deviation, median, first and third quartiles (Q1-Q3), and minimum and maximum values. All raw data will be presented to the original number of decimal places. Where appropriate, means, medians, and confidence intervals will be presented to 1 more decimal place than in the raw data. Likewise, standard deviations will be presented to 2 more decimal places than in the raw data.

Summary statistics for categorical variables will contain count and percentage. Percentages will be presented to one decimal, except for one hundred percent, which will be presented as 100%. Unless otherwise specified, percentages for baseline summaries will be based on the total number of subjects in the respective analysis set, whereas percentages for post-baseline summaries will be based on the total number of subjects assessed (i.e. with non-missing values) in the respective analysis set as specified in Section 8.

Confidence intervals for means and percentages will be calculated when appropriate and will be 2-sided at the 95% level unless otherwise specified. p -values will be reported to 3 decimal places where applicable; p -values less than 0.001 will be reported as $p < 0.001$.

All data will be listed individually by subject, sorted by Subject Identifier (ID) and date of assessment or start date as applicable. In general, listings will be based on SAS except for eligibility and enrollment information including inclusion/exclusion criteria and informed consent, visit/telephone contact information, demographics, adverse events, and death, which will be based on screened subjects. Listings may include age, sex, indication of whether the subject has qualified for analysis set (e.g., SAS or FAS), or analysis record (e.g. Yes if used in analysis), where applicable. In case of indication for analysis set, listings will be generally sorted by subjects qualifying for SAS first before those not qualifying for SAS amongst screened subjects.

For efficacy parameters, the absolute and relative change from baseline will be derived as follows:

- Absolute change from baseline = $X_i - X_0$
- Relative change from baseline = $100 * (X_i - X_0) / X_0$

Where X_i = observed/assessed value at a given analysis timepoint, whereas X_0 = observed/assessed value at baseline.

All analyses will be performed using [REDACTED]

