7.4 Efficacy analysis

For all continuous efficacy endpoints mean change from baseline to end of treatment will be presented with simple 95% confidence interval and a t-test of no change from baseline. This will be done both for absolute and relative change. Due to the relatively small sample size, a non-parametric estimate of the change from baseline to end of treatment for each endpoint will be derived using the one-sample Hodges-Lehmann median estimator with corresponding 95% confidence interval.

As some of the continuous endpoints can be close to or below zero at baseline (e.g., absorption of energy), the relative change of such endpoints should be interpreted with great caution as the analysis can lead to meaningless results.

Responder endpoints will be tabulated with number of subjects and percentages of subject in FAS.

Other categorical endpoints will be tabulated with number of subjects and percentages of observed subjects. For ordinal endpoints change from baseline will also be calculated and tabulated.

For endpoints related to nutritional status and nutritional absorption sensitivity analyses will be made excluding subjects missing more than 20% of the planned

injections prior to the time of analysis. Hence the number of injections leading to exclusion will be one at Week 4, six at Week 24, and 11 at Week 52.

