7.2 SECONDARY ENDPOINTS

Efficacy endpoints related to PS volume

- Relative change from baseline in actual weekly PS volume at Weeks 4, 24 and 52
- Absolute change from baseline in actual weekly PS volume at Weeks 24 and 52
- Subjects who achieve a reduction of at least 1 day per week of PS from baseline at Weeks 24 and 52
- Clinical responders (20% reduction of PS volume from baseline) at Weeks 24 and 52
- Subjects reaching enteral autonomy at Weeks 24 and 52
- Energy reduction in the Parenteral Nutrition (PN) from baseline at Weeks 24 and 52

Efficacy endpoint related to nutritional, fluid (wet weight) and electrolyte absorption

- Absolute change in absorption of energy over MB periods from baseline to Week 48 (applicable to the protocol version 4)
- Relative change in absorption of energy over MB periods from baseline at Week 48
- Change in absorption of macronutrients over MB periods from baseline at Week 48

- Absolute change in absorption of energy over MB periods from baseline at Week 4
- Change in absorption of macronutrients over MB periods from baseline at Week 4
- Changes in urine output and urinary electrolytes (sodium, potassium, calcium and magnesium) over MB periods from baseline at Week 4 and at Week 48

Patient reported outcomes (PRO)

- Changes from baseline in [REDACTED] at Weeks 24 and 52
- Patient Global Impression of Change (PGIC) at Weeks 24 and 52
- Changes from baseline in Patient Global Impression of Treatment Satisfaction (PGI-TS) at Weeks 24 and 52
- Changes from baseline in Patient Global Impression of Satisfaction with PS (PGI-SPS) at Week 24 and 52
- Changes from baseline in Patient Global Impression of PS Impact (PGI-PSI) at Week 24 and 52.

PK/PD related endpoints

- Trough plasma concentration
- Plasma citrulline levels

Safety endpoints (applicable to the protocol version 3)

- AESI
- Clinical chemistry, hematology, hemostasis, ADAs, and urine analysis
- AEs

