9.7.2 ANALYSIS OF SECONDARY ENDPOINTS

9.7.2.1 ANALYSIS OF SECONDARY ENDPOINTS RELATED TO PS VOLUME

Subject diary data will be used to obtain PS volume information for analyses. Subjects are to complete diary prior to a scheduled visit. If a subject's e-diary data is not available, PS data recorded at the site will be used for analyses. If a subject has issues/difficulties using the e-diary, PS volume data will be captured in the paper diary and will be entered into the electronic data capture (EDC) system at a trial visit.

The relative as well as absolute change in actual weekly PS volume from baseline to every 4 weeks until Week 52 will be summarized by descriptive statistics. p -values and Hodges-Lehmann median estimator along with 95% CI will be produced for Week 24 and Week 52 as defined in the introduction of Section 9.7. The sum of daily PS volume (including extra fluids) from weekly PS diary data recorded for the corresponding analysis timepoint will be used for analysis.

The proportion (%) of subjects who have achieved a reduction of at least 1 day per week of PS from baseline at every 4 weeks until Week 52 will be produced. Subjects will be considered to

have a reduction of at least one day per week of PS from baseline (incl. extra fluids) if the number of days with PS from weekly PS diary data recorded for the corresponding analysis timepoint is smaller compared to the number of days with PS from weekly PS diary data for the baseline.

In addition, the proportion (%) of clinical responders (20% reduction of PS volume from baseline) at every 4 weeks until Week 52 will be produced. Subjects will be considered to be a clinical responder if the relative change from baseline in weekly PS volume is $\leq -20\%$ for the corresponding visit.

For above analyses, missing weekly PS data from diary (e.g. volume, frequency, etc) will be imputed to 0 in case of PS being weaned off (Refer to Section 9.3.).

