10. DEVIATIONS FROM ANALYSIS DESCRIBED IN THE PROTOCOL

The following update has been made from the planned analysis defined in the protocol to align the safety analysis plan as defined in the TA799-007 study.

- In the protocol, TEAE is defined as all AEs occurring after first dose of trial medication and up to the 4 weeks follow-up visit. However, for the safety analysis, TEAE will be defined as any adverse events that started on or after the first dose of trial medication (i.e. no longer depends on 4 weeks follow-up visit).

There is one deviation from the planned analysis described in the protocol. According to the protocol, the primary endpoint AESIs are to be derived based on SMQ or CQs. Sponsor issued NTF (See [Appendix 4: Addendum to Statistical Analysis Plan](#)), to clarify that AESI will be identified by using the investigator's assessment, reported in eCRF for analysis.

In addition, the following list contains typographical error (typo) corrections from the protocol that have been made to this SAP for clarity:

- The protocol refers to 'change in absolute absorption'. It is clarified in SAP that this refers to 'absolute change from baseline' in comparison to 'relative change in absorption'. Note: This SAP uses 'absolute change from baseline' and 'change from baseline' interchangeably.
- One of the secondary efficacy endpoints defined in the protocol is 'clinical responder at Week 52' but unlike the protocol synopsis and Section 1.5.2.2 of the protocol, Section 7.1.2 of the protocol indicated Week 48 instead of Week 52. This typo has been corrected to Week 52 in this SAP.
- One of the efficacy endpoints defined in the protocol is 'change in dietary intake of wet weight, energy, macronutrients, fluid, electrolytes (sodium, potassium, calcium, and magnesium) from baseline at Week 4 and Week 48', but this 'fluid' is a part of weight as oral fluid; hence, this text, 'fluid', is omitted in this SAP.
- One of the efficacy endpoints defined in the protocol is "change in fecal excretion of wet weight, energy, macronutrients, fluid and electrolytes (sodium, potassium, calcium, and magnesium) from baseline at Week 4 and Week 48", but this "fluid" is a part of wet weight (urine), which has already been covered by urine output as a part of the secondary efficacy endpoint; hence, the text, 'fluid', is omitted in this SAP.

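### The SAP's default denominator (subjects with data) applies to the 20% clinical-responder rate, where the protocol specifies the full FAS, and the change is not declared

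*SAP*

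**What the plan says.** Protocol 7.4 (Efficacy analysis) treats two kinds of endpoint differently, in adjacent sentences: "Responder endpoints will be tabulated with number of subjects and percentages of subject in FAS", and then "Other categorical endpoints will be tabulated with number of subjects and percentages of observed subjects".

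SAP 9.1 (General conventions) has one rule for all post-baseline percentages where nothing else is stated: "percentages for post-baseline summaries will be based on the total number of subjects assessed (i.e. with non-missing values) in the respective analysis set". The sentence then refers to SAP Section 8, which assigns efficacy analyses to the FAS.

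SAP 7.2 lists one secondary endpoint by the name of responder: "Clinical responders (20% reduction of PS volume from baseline) at Weeks 24 and 52". SAP 9.7.2.1 says "the proportion (%) of clinical responders (20% reduction of PS volume from baseline) at every 4 weeks until Week 52 will be produced" and sets the cut-off at a relative change of −20% or lower. It gives no denominator and no rule for a subject without data at the visit.

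SAP Section 10 reports a new definition of treatment-emergent events and then says "There is one deviation from the planned analysis described in the protocol", meaning how adverse events of special interest are identified. A list of typographical corrections follows. None of these entries concerns the responder denominator.

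**The concern.** The protocol and the SAP prescribe different denominators for the same percentage. The protocol's contrast between FAS and observed subjects suggests that the full denominator for responders was a deliberate choice. A programmer following the SAP would produce a different figure, and a reader of the report would not be told.

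The difference runs in one direction. Under SAP 9.3, missing diary data become 0 only for subjects recorded as weaned off PS, and those subjects count as responders. A subject still on PS with no data leaves the denominator. With about nine subjects, each such loss moves the rate by several points.

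**Working it through.** The documents give no responder rate or missing-data count to reproduce, so the check compares the texts and then sizes the effect under stated assumptions.

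**Which rule reaches the endpoint**

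1. Protocol 7.4 makes the rate r/FAS, where r is the number of responders.
2. SAP 9.1 makes it r/(FAS − m), where m is the number of FAS subjects without data at that visit. Section 8 does not restore the full denominator: it fixes the population, and 9.1 then takes the assessed subjects within it.
3. SAP 9.7.2.1 contains no override. The SAP does state denominators where it wants particular ones, for example in disposition (9.4), laboratory shift tables (9.8.3) and immunogenicity (9.8.5).
4. Section 10 corrects the week of this same endpoint (48 to 52) but does not mention its denominator.

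**Whether m can exceed 0**

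- The FAS needs only one valid post-baseline efficacy point (SAP 8.1), so a member can lack Week 24 or Week 52 data.
- Protocol 3.5 asks for follow-up after discontinuation, SAP 9.7.2.1 allows site-recorded or paper-diary data, and SAP 9.2 lets end-of-trial data fill a missing visit. These reduce m without guaranteeing 0. Subjects entering the extension have no end-of-trial assessments (SAP 4.1).
- For PS volume collected after withdrawal from trial visits, SAP 9.8.4 promises only a listing. It does not say whether those values enter the responder table.

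**Direction**

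A weaned-off subject with baseline volume X₀ has relative change 100 × (0 − X₀)/X₀ = −100%, which is a response. Missing subjects who are not weaned off add nothing to r and leave the denominator. Hence SAP rate / protocol rate = FAS/(FAS − m) ≥ 1 whenever r is at least 1.

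**Size**

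Inputs:
- SAP Section 2 reports 2 + 7 = 9 enrolled. FAS = 9 assumes all of them qualify; FAS = 8 assumes one does not.
- m = 0 to 2 is assumed. Protocol 7.2 expects 8 of 10 to complete, which is only a guide, because non-completion is not the same as missing data.
- r is assumed.

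Multipliers:
- FAS = 9: 9/8 = 1.125 for m = 1; 9/7 = 1.286 for m = 2.
- FAS = 8: 8/7 = 1.143 for m = 1; 8/6 = 1.333 for m = 2.

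| FAS | r | Protocol rule (any m) | SAP rule, m = 1 | SAP rule, m = 2 |
|---|---|---|---|---|
| 9 | 2 | 22.2% | 25.0% (+2.8 points) | 28.6% (+6.3) |
| 9 | 4 | 44.4% | 50.0% (+5.6) | 57.1% (+12.7) |
| 9 | 6 | 66.7% | 75.0% (+8.3) | 85.7% (+19.0) |
| 8 | 4 | 50.0% | 57.1% (+7.1) | 66.7% (+16.7) |

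With m = 0 the two rules agree in every row. For scale, the exact (Clopper-Pearson) 95% confidence interval for 4/9 is 13.7% to 78.8%, much wider than any of these shifts.

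**The case against.** **The protocol may itself be the exception.** The SAP default yields to other specifications, and SAP Section 2 says the analysis follows protocol version 4 for all subjects. On that reading protocol 7.4 still controls and Section 10 had nothing to declare. This does not hold: that sentence settles which protocol version's endpoints apply, because the French site stayed on version 3. It does not displace an explicit SAP rule on percentages.

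**Unseen documents may resolve it.** The default sentence ends "in the respective analysis set as specified in Section 8", and Section 8 refers to the sponsor's Note to File, which supersedes both the SAP and the mock-up tables. This stands as a limit. Section 10 mentions the Note only for adverse events of special interest, but Sections 6 and 8 also cite it for further changes.

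**Missing data should be rare, and the result is easy to recompute.** Both points stand. The endpoint is secondary and descriptive with no decision rule, and counts and subject listings are planned. They limit the importance of the conflict without removing it.

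**The largest shift is generous.** FAS = 8 with two missing means 3 of 9 enrolled subjects contribute nothing at the visit, more than the protocol's 2 in 10 non-completers. That is fair, and the row is best read as an upper illustration.

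**Counting missing as not achieved could be seen as replacing values, contrary to protocol 7.8.** No PS value is filled in. Dividing responders by the whole FAS, as protocol 7.4 requires, already has this effect.

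**Conclusion.** The concern holds. As written, the SAP computes the 20% clinical-responder percentage on subjects with data, the protocol specifies the FAS, and the difference is undeclared. The SAP rate is inflated by FAS/(FAS − m). For an assumed FAS of 9 with 4 responders that is +5.6 points with one subject missing and +12.7 with two; with none missing it is zero. FAS size, responder count and missing count are all assumptions.

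The conclusion is limited to the 20% endpoint. Protocol 7.4 does not say whether the proportions with at least one PS day fewer per week, or with enteral autonomy, are responder endpoints. If they are other categorical endpoints, the SAP already matches the protocol for them. The conclusion also depends on the Note to File and the mock-up tables not having fixed the denominator. It should be corrected, though it would not change any decision in the trial.

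**What to change.** 1. Check whether the Note to File or the mock-up tables already set the denominator. If so, carry that wording into SAP 9.7.2.1.
2. If not, state in 9.7.2.1 that the 20% clinical-responder percentage uses all FAS subjects, with a subject lacking data at the visit counted as not having achieved the response. Show the observed-case percentage beside it.
3. If the assessed-subject denominator is intended, declare it in Section 10 as a departure from protocol 7.4 and give the reason.
4. State whether the one-day-reduction and enteral-autonomy proportions are responder endpoints under protocol 7.4, and apply the matching denominator.

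The cost is one or two sentences for the responder rule, a short classification of the other two proportions, and one denominator in the table program. The reported rate may be slightly lower, and a subject missing for unrelated reasons counts against the response; the observed-case column shows how much that matters.

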9.2 DEFINITION OF BASELINE, TRIAL VISITS, AND VISIT WINDOWS

The baseline is the last available assessment/observation prior to first trial treatment (i.e. first administration of apraglutide). For assessments done on the same day as the first trial treatment, the time of assessment should be used to recognize whether or not the assessment was done prior to the first trial treatment. Otherwise, when the time of assessment is not available, last available assessments on or prior to the date of first trial treatment will be

considered as baseline since assessments are to be performed prior to dosing on the day of the first IMP administration according to the schedule of assessments in the protocol.

For evaluation of MB parameters, all relevant data measured over the MB period at the scheduled visit will be considered as the analysis timepoint. This applies to baseline, Week 4, and Week 48. The detailed derivation of baseline MB period data can be found in Section 9.7. Except for EOT visit data for efficacy analyses, by-visit efficacy data will be analyzed based on eCRF visits.

For all efficacy analyses, the EOT visit data will be mapped to a visit as defined below and will be only used to replace any missing by-visit efficacy data:

Table 9.2.1: Data Mapping Scheme

Visit	Analysis timepoint	Target day*	
4	Week 2	Day 15	
5	Week 4	Day 29	
6	Week 8	Day 57	
7	Week 12	Day 85	
8	Week 16	Day 113	
9	Week 20	Day 141	
10	Week 24	Day 169	
11	Week 28	Day 197	
12	Week 32	Day 225	
13	Week 36	Day 253	
14	Week 40	Day 281	
15	Week 44	Day 309	
16	Week 48	Day 337	
17	Week 52	Day 365	

*based on the relative days from the first trial treatment where the relative days from the first trial treatment = date of assessment or event – date of first trial treatment + 1, when both dates are known for assessments or events started on or after the day of the first trial treatment. (e.g., Relative Study Day 1 = the first study dosing day)

For safety data analysis, by-visit data will be analyzed based on the assigned analysis visit based on the data mapping scheme above. If more than one assessment falls into allowed time window the closest to the target date will be used. If two values are equidistant from the planned visit/assessment date, the first value will be used.

The citrulline and apraglutide plasma concentration data will be analyzed by scheduled visit based on eCRF visit (including EOT where applicable).

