2.2.4 Follow-up Period

Safety follow up assessments will be performed 4 weeks (± 1 week) after the last dose (EOT), except for subjects continuing into the LTE.

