5.2.8 Visit 18 (End-of-Trial Visit)

This visit is scheduled at 4 weeks after last dose of IMP for all subjects who opt not to participate in the LTE. In case a subject terminates the trial prematurely for whatever reason, this visit will be scheduled as an EOT visit at 4 weeks after the final IMP dose.

- Data will be recorded for:
 - Changes in concomitant medications
 - Prescribed PS volume and composition
 - Change in eating/appetite
 - Patient reported outcomes
 - Investigator narrative
- A colonoscopy including removal of any polyps or colonography will be done within ± 3 weeks of the EOT visit, only for subjects that terminate early. The assessment will be done only if they have received at least 8 weeks of treatment (i.e., eight doses).
- Full physical examination
- Twelve-lead ECG
- Vital signs (systolic and diastolic blood pressure, heart rate, and axillary temperature)
- Body weight
- Blood samples will be collected for:
 - Clinical chemistry including liver enzymes
 - Hematology
 - Hemostasis
 - Pharmacokinetics
 - Citrulline
 - Anti-drug antibodies
 - Serum pregnancy test for premenopausal women
- Urine sampling for urinalysis
- Any new AEs will be recorded and assessed, and existing AEs will be followed up (see Section 6)

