7.8 Handling of Missing Values

Missing values will not be replaced.

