4.1 TRIAL DESIGN

This is a repeated-dose, open-label trial investigating the efficacy, safety, PD, and pharmacokinetics (PK) of apraglutide in subjects with SBS-IF and CIC. The subjects will receive a subcutaneous (SC) dose of 2.5 mg or 5 mg apraglutide once weekly for 52 weeks. Safety follow-up assessments will be performed 4 weeks (\pm 1 week) after the last dose.

Subjects will undergo three 72-hour MB evaluations at baseline, Week 4, and Week 48. For the first 4 weeks, up to the completion of the second MB study, the PS should not be changed. PS volume can be reduced for safety reasons but all possible attempts should be made to return to the baseline PS prescription for the second MB period.

Subjects that do not complete the baseline and 4-week MB evaluation and/or do not receive all 4 doses of Investigational Medicinal Product (IMP), per protocol, may be replaced. Subjects that withdraw after the 4-week MB evaluation may not be replaced.

At each visit, starting after Week 4, the PS volume will be reviewed and adjusted by the investigator taking into account the protocol-defined algorithm for PS volume reduction, based on changes in urine output of 10% or greater.

For subjects with change in urine output not higher than 10%, cases will be adjudicated by the participating investigators who will review the clinical status of participants to assess if PS volume reduction is warranted. The three investigators will make recommendations for the safety of subjects and with the objective to standardize and harmonize decisions on PS volume reduction and weaning across the three sites.

The safety follow-up is planned at the end of trial (EOT) visit, 4 weeks after the last IMP dose. If trial treatment is discontinued permanently, assessments will be performed at EOT visit, 4 weeks after the last dose. If the subject enters the long-term Safety and Clinical Outcomes extension trial (LTE, TA799-012), no EOT assessments will occur.

In case a subject discontinues or withdraws prematurely from the trial treatment for any reason after receiving at least one dose of IMP, subjects will be asked to continue to participate in the trial beyond the EOT visit according to the schedule of assessments (with the exception of IMP administration).

The schedule of assessments are found in [Appendix 1: Schedule of Assessments](#).

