9.3 HANDLING OF MISSING DATA

In general, missing values will not be replaced, and observed values will be used for analyses unless specified in the sections below.

For the calculation of duration of SBS disease history, if there are any partial dates of SBS disease history, the first day and/or month of the year will be assumed for a missing day and/or month for the purpose of duration calculation based on the worst case scenario approach.

For medication or therapeutic interventions with imprecise/partial date(s), the first day/month of the year will be assumed for unknown day/month of the start date, and the last day/month of the

year will be assumed for unknown day/month of the stop date to categorize medications or therapeutic interventions as concomitant for the worst case scenario.

For events with imprecise/partial date(s), unless the start or end date of the known month or year is before the date of the first trial treatment, all events will be deemed as treatment-emergent adverse events (TEAEs) as opposed to pre-existing AEs.

For analyses of safety, missing data about AE relationship to trial treatment, intensity, seriousness, and outcome will be assumed to be 'related to the trial treatment', 'severe', 'serious', and 'not recovered/not resolved', respectively, based on the worst case scenario.

For analyses of efficacy, weekly PS data from diary may be missing in case of PS being 'weaned off'. In this case, missing weekly PS diary data (e.g. volume, frequency, total time of infusion etc.) will be imputed to 0 for analyses based on 'weaned off' information according to the PS prescription eCRF. Once 'weaned off' is recorded in eCRF at a visit, sites are not asked to repeat this data in the next visit. Hence, for analysis, 'weaned off' data will be carried forward to the next analysis timepoint(s) where applicable based on subjects' visit information until indicated otherwise (i.e. no longer reported as 'weaned off').

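### The SAP fills missing by-visit efficacy values with End-of-Trial data taken about 4 weeks after the last dose, contrary to Protocol 7.8 and not listed in SAP Section 10

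*SAP*

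**What the plan says.** SAP 9.2 analyses by-visit efficacy data by eCRF visit, with one exception. EOT data are assigned to one of the timepoints in Table 9.2.1 (Weeks 2 to 52) and "will be only used to replace any missing by-visit efficacy data". They do not overwrite an observed value.

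The timing of EOT is consistent across the documents. SAP 4.1: "The safety follow-up is planned at the end of trial (EOT) visit, 4 weeks after the last IMP dose". Protocol 2.2.4 gives the same interval with a window of ±1 week. Protocol 5.2.8: "This visit is scheduled at 4 weeks after last dose of IMP for all subjects who opt not to participate in the LTE". For subjects who enter the extension trial (LTE), SAP 4.1 states that "no EOT assessments will occur".

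Protocol 7.8 sets the missing-data rule without exception: "Missing values will not be replaced". SAP 9.3 keeps it as the default: "In general, missing values will not be replaced, and observed values will be used for analyses unless specified in the sections below". SAP Section 10 covers departures from the protocol. It reports a changed definition of treatment-emergent events, then says "There is one deviation from the planned analysis described in the protocol" (how events of special interest are identified), then lists typographical corrections. EOT replacement is not among them.

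**The concern.** EOT is a safety follow-up visit in a different treatment state from the visits it may fill. The protocol's definition of enteral autonomy itself treats Visit 17 (Week 52) as the last visit under trial treatment. A Week 52 summary that contains EOT values mixes results from about one week after a dose with results from about four weeks after a dose, and the reader of the table cannot see which are which.

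The rule also applies unevenly. A subject who enters the LTE and misses Week 52 stays missing, while a subject who declines the LTE and misses the same visit can be filled.

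One questionnaire makes the problem plain. The Patient Global Impression of Treatment Satisfaction (PGI-TS) asks about satisfaction with the trial medication over the past 7 days. At EOT none was given in those 7 days, yet the answer could be reported as a Week 52 score.

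**Working it through.** **1. The rules side by side.** Protocol 7.8 has no replacement and no exception. SAP 9.3 has no replacement unless a later section says otherwise. The EOT rule stands in 9.2, before that sentence, so it conflicts with the protocol and is not covered by the SAP's own exception clause. Section 10 is silent on it.

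**2. Target days.** Every row of Table 9.2.1 follows 7 × week + 1. For example, Week 24 = 7 × 24 + 1 = Day 169, and Week 52 = 7 × 52 + 1 = Day 365.

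**3. A completer who does not enter the LTE.** Weekly dosing for 52 weeks is read as 52 injections in Weeks 0 to 51, because the Schedule of Assessments shows no injection at Visit 17.
- Last dose: 7 × 51 + 1 = Day 358.
- EOT: 358 + 28 = Day 386, or Days 379 to 393 with the ±7-day window.
- Nearest target: Week 52, Day 365. Nearest-target mapping is an assumption, since no efficacy windows can be read in the table.
- Week 52 visit relative to last dose: 365 − 358 = 7 days.
- EOT value relative to last dose: 28 days (21 to 35).
- EOT is later than the Week 52 target by 386 − 365 = 21 days (14 to 28).

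**4. An early discontinuer.** With the last dose in Week j (j = 0 to 50), the last dose is on Day 7j + 1 and EOT on Day 7j + 29. Ties are given to the earlier visit (an assumption).
- Week 24 would be filled for last doses in Weeks 19 to 22. Those doses fall on Days 134 to 155, so Day 169 is already 14 to 35 days after the last dose.
- At the nominal 28 days, 0 of the 51 possible last-dose weeks map EOT to a visit within 7 days of the last dose.
- Taking each whole day of the ±7-day window gives 51 × 15 = 765 combinations, of which 12 map to such a visit. All 12 are exact ties at the early edge of the window.

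The filled slot is therefore almost always off drug itself.

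**5. Which endpoints can be filled.**

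| Data | Collected at EOT? | Can be filled? |
|---|---|---|
| Prescribed PS and PN energy, weaning status | Yes, with the PS prescription | Yes |
| Questionnaires, including PGI-TS and the GLP-2 injection items | Yes | Yes |
| Body weight | Yes | Yes |
| Actual weekly PS volume | Diary not ticked at Visit 18 | Only if site-recorded PS is used (SAP 9.7.2.1) |
| Energy, macronutrient and wet-weight absorption; balance-period urine; DEXA | No | No |

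**6. Weight of one value.** The SAP reports 2 + 7 = 9 enrolled subjects. If all 9 are analysed, one value carries 1/9 = 11.1% of the mean. If the other 8 have mean m and the EOT value is x, filling changes the reported mean from m to (8m + x)/9, a shift of (x − m)/9. The documents give neither x nor m.

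**The case against.** Several counter-arguments have force.

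- **Windows.** The last column of Table 9.2.1 is blank in the available text and may have held windows. If Week 52 closed at Day 365 + 14 = 379, only an EOT visit on the first day of its allowed range would qualify. The Week 52 case is therefore conditional.
- **Off-drug data are already in the plan.** Protocol 3.5 asks discontinuers to attend scheduled visits to Week 52 without drug. For them, an EOT value mapped by date is an observed off-drug value placed in an off-drug slot. A reader might infer that the rule contaminates purely on-drug endpoints at Weeks 24 and 52; the documents do not support that.
- **PS volume.** A reader might infer that prescribed volume would be reported as actual volume. SAP 9.7.2.1 refers only to PS data recorded at the site. Protocol 5.2.8 records prescribed PS at Visit 18, but Protocol 5.1.7 asks for actual PS in the 7 days before each visit except Visit 3. The texts are mixed, so this step is possible but not established.
- **Questionnaires.** Not all are compromised. The global impression of change refers to the whole time since starting the medication. The GLP-2 injection items look back 4 weeks, which can include the last injection if EOT is held early.
- **Note to File.** It supersedes the SAP and cannot be seen. SAP Sections 6, 8, 9.8.2 and 10 point to it and 9.2 does not, so nothing visible suggests that it changes this rule, but that cannot be excluded.
- **Later reporting.** Protocol 7.9 requires deviations to be described in the trial report, and all data are listed by subject.

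These points narrow the scope. They do not remove the conflict with Protocol 7.8 or the omission from Section 10.

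**Conclusion.** The point holds in limited form. The EOT replacement rule contradicts Protocol 7.8 and is missing from the SAP's list of departures. It is most harmful for Week 52 in completers outside the LTE, if no window in Table 9.2.1 prevents it, and PGI-TS is the clearest case. For early discontinuers it is an undisclosed replacement rather than a mixing of treatment states. LTE entrants cannot be filled at all.

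Each filled value carries 11.1% of a 9-subject mean. A reader might go on to assume a loss of effect off drug and quote a resulting bias. The documents give no rebound figure. Moreover, without the rule the reported result would be the mean of the remaining 8, not a mean that includes the subject's unobserved on-drug value. Direction and size therefore cannot be stated.

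The conclusion rests on 52 injections in Weeks 0 to 51, nearest-target mapping, all 9 enrolled subjects being analysed, and the unseen Note to File leaving 9.2 unchanged. The primary endpoints are safety endpoints and are not touched by this efficacy rule.

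**What to change.** Make the observed-only analysis, without EOT replacement, the main efficacy analysis. Show EOT as its own row, labelled as four weeks after the last dose. SAP 9.2 already handles citrulline and drug concentrations this way, with EOT kept as a separate visit.

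If EOT replacement is kept, present it only as a labelled supplementary analysis. State its mapping windows and the endpoints affected, exclude PGI-TS and the GLP-2 injection items, and list it in SAP Section 10.

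The cost is a change of SAP wording and a few fewer observations at some timepoints. One of these could be a discontinuer's only late value, which would still appear in the EOT row and the listings.
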